Primary objective (2) is to evaluate ORR in subjects who fulfill the eligibility criteria for Cohort A and with higher expression of program cell death-ligand protein 1 (PD-L1) in tumor tissue samples. It is expected that higher PD-L1 expression in tumor tissue will be associated with better clinical responses to pembrolizumab (refer to Section 4 for background and rationale). In order to achieve this primary objective, a PD-L1 expression cutpoint will first be established with a goal to enrich the population for better clinical benefit. The cutpoint will be determined during the planned interim analysis using the clinical efficacy data and PD-L1 expression data from the first 100 enrolled Cohort A subjects. This data set is designated as the “training set” (refer to Section 8.7 on the approach for determining the PD-L1 cutpoint). In order to confirm the association of higher PD-L1 expression with increased clinical activity by pembrolizumab treatment, another 150 subjects who fulfill eligibility criteria for Cohort A will be enrolled, which is designated as the “confirmation set”. Cohort A will therefore, enroll a total of 250 subjects. Based on the established PD-L1 cutpoint from the training set, subjects in the confirmation set will be assigned into the subgroup with PD-L1 expression above or equal to the cutpoint (i.e., Cohort A PD-L1_H) or the subgroup with PD-L1 expression below the cutpoint (i.e., Cohort A PD-L1_L). Enrollment into Cohort A will not be interrupted for interim analysis. However, in order to ensure data integrity, samples from the “confirmation set” will not be assessed for PD-L1 expression until the cutpoint has been established and the assay has been confirmed. Based on the prevalence data regarding higher PD-L1 expression, the total enrollment of Cohort A may be increased to up to 280 to ensure a minimum of 60 subjects from the confirmation set (see below) will have PD-L1 expression above the expected cutpoint.

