Approximately 75 subjects will be enrolled into Cohort B regardless of PD-L1 expression status. Primary objective (3) is to evaluate ORR in all enrolled subjects who fulfill the eligibility criteria for Cohort B. This group is designated as Cohort B-All Comer group. Primary objective (4) is to evaluate ORR in subjects enrolled into Cohort B who have tumor tissue PD-L1 expression above the clinical cutpoint established from the Cohort A training set. The population supporting primary objective (4) is designated as Cohort B PD-L1_H group. Tumor tissue samples from Cohort B will not be evaluated until a cutpoint has been established from Cohort A training set.

As part of the inclusion criteria, all subjects must provide a tumor tissue sample collected either from a recent biopsy or prior cytoreductive surgery in order to be enrolled. Part of the tumor tissue sample will be submitted to a designated central laboratory for assessing PD-L1 expression via an immunohistochemistry (IHC) assay. PD-L1 positivity is determined using the combined positive score, which is defined as the percent PD-L1 positive cells counting tumor cells, immune-infiltrating cells and cells from adjacent stroma relative to total tumor cells. Details will be provided in a separate document.

Clinical cut-off for interim analysis will be at least 4 months after the one-hundredth Cohort A subject has been enrolled to allow adequate clinical follow up. For each designated study population (i.e., Cohort A-All Comer, Cohort A PD-L1_H, or Cohort B), the clinical cut-off for the final analysis of the primary endpoint ORR will be at least 8 months after the last subject for each population has been enrolled. The final clinical cut-off for the study (i.e., study completion) will be 3 years after the last subject is enrolled for final overall survival (OS) analysis. Refer to Sections 3.2 and 3.3 for details regarding secondary and exploratory study objectives, and [Figure 1](#) in Section 2.2 for illustration of the overall study design.

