3.0 OBJECTIVE(S) & HYPOTHESIS(ES)

3.1 Primary Objective(s) & Hypothesis(es)

In subjects with advanced ROC:

- 1) **Objective:** To evaluate clinical anti-tumor activity of pembrolizumab monotherapy based on ORR as assessed by BICR per RECIST 1.1 in Cohort A-All Comer group as defined in Section 2.1
- 2) **Objective:** To evaluate clinical anti-tumor activity of pembrolizumab monotherapy based on ORR as assessed by BICR per RECIST 1.1 in Cohort A-PD-L1_H subgroup, as defined in Section 2.1, using a PD-L1 expression cutpoint established in the training set.
- 3) **Objective:** To evaluate clinical anti-tumor activity of pembrolizumab monotherapy based on ORR as assessed by BICR per RECIST 1.1 in Cohort B-All Comer group as defined in Section 2.1
- 4) **Objective:** To evaluate clinical anti-tumor activity of pembrolizumab monotherapy based on ORR as assessed by BICR per RECIST 1.1 in Cohort B PD-L1_H subgroup, as defined in Section 2.1, using a PD-L1 expression cutpoint established in the training set from Cohort A

The primary objectives will focus on estimation of ORR, and no formal hypothesis testing is planned. If the operating characteristics associated with a single biomarker cutpoint are not sufficiently optimized, up to 2 biomarker cutpoints may be carried forward for efficacy endpoint analyses (see Section 8.6.1).

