8.0 STATISTICAL ANALYSIS PLAN

This section outlines the statistical analysis strategy and procedures for the study. If, after the study has begun, but prior to any unblinding/final database lock, changes made to primary and/or key secondary hypotheses, or the statistical methods related to those hypotheses, then the protocol will be amended (consistent with ICH Guideline E-9). Changes to exploratory or other non-confirmatory analyses made after the protocol has been finalized, but prior to final database lock, will be documented in the supplemental Statistical Analysis Plan SAP (sSAP) and referenced in the Clinical Study Report (CSR) for the study. Post-hoc exploratory analyses will be clearly identified in the CSR. The sSAP will also document the detailed biomarker analysis strategy including determination of the PD-L1_H cut-off selection.

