8.5 Analysis Populations

8.5.1 Efficacy Analysis Populations

Cohort A

The Full Analysis Set (FAS) population for All Comers, which consists of 180 first enrolled subjects in Cohort A who receive at least 1 dose of study treatment and with measurable disease at baseline, will serve as the primary population for the analyses of efficacy data for

Cohort A All Comers. The FAS population for PD-L1_H subgroup in Cohort A, which includes the subjects in the confirmation set above the PD-L1 cut-off, will be used for the analyses of efficacy data for PD-L1_H subjects in Cohort A. Supportive analyses of efficacy will be conducted in the All Subjects as Treated (ASaT) population, defined as all enrolled subjects in all comers or PD-L1_H in the confirmation set respectively who receive at least 1 dose of study medication (not applicable if there is no difference with the FAS population).

Cohort B

The FAS population consists of all subjects in Cohort B who receive at least 1 dose of study treatment and with measurable disease at baseline. The FAS population for PD-L1_H subgroup in Cohort B, which includes the subjects in Cohort B above the PD-L1 cut-off, will be used for the analyses of efficacy data for PD-L1_H subjects in Cohort B.

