cut-off) vary with putative cut-offs. A cut-off that maintains high NPV (e.g., above 90%) while achieving meaningful enrichment of response and largely capturing patients showing durable clinical benefit is ideal. The profiles of PPV, NPV, and the percentage of patients above a given cut-off along with intervals quantifying the uncertainty in those profiles will be estimated as a function of potential cut-offs. Receiver operating characteristic curve analysis will also be used to understand the sensitivity and specificity profile and examine cut-offs that might be suggested based on the ROC curve and their appropriateness with regard to PPV and NPV. If the operating characteristics associated with a single biomarker cutpoint are not sufficiently optimized, up to 2 biomarker cutpoints may be carried forward for efficacy endpoint analyses (i.e., a biomarker positive cutpoint and a biomarker high positive cutpoint), as has been implemented in other tumor types within the pembrolizumab program (e.g., bladder cancer) [44]. Details of the biomarker analysis strategy will be documented in the sSAP.

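### Does PD-L1_H, the population for primary objectives 2 and 4, lack a single definition because a second cutpoint is allowed and the boundary wording varies?

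*Combined protocol and SAP*

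**What the plan says.** Protocol Section 2.1.1 sets the cutpoint from the first 100 Cohort A subjects. It then splits the confirmation set in two: "subjects in the confirmation set will be assigned into the subgroup with PD-L1 expression above or equal to the cutpoint (i.e., Cohort A PD-L1_H". Everyone under the cutpoint goes to PD-L1_L, so no subject is left unassigned. Total Cohort A enrolment "may be increased to up to 280 to ensure a minimum of 60 subjects from the confirmation set"; the 60 are those over the expected cutpoint. For Cohort B the same section describes the high group as having "tumor tissue PD-L1 expression above the clinical cutpoint established from the Cohort A training set". Section 8.5.1 gives the Cohort A analysis population as the one "which includes the subjects in the confirmation set above the PD-L1 cut-off", and sSAP Section 3.5.1 repeats this.

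The second cutpoint appears in two places. Section 3.1, directly under the primary objectives, gives the condition: "If the operating characteristics associated with a single biomarker cutpoint are not sufficiently optimized". Section 8.6.1 repeats the condition and names the pair: "up to 2 biomarker cutpoints may be carried forward for efficacy endpoint analyses (i.e., a biomarker positive cutpoint and a biomarker high positive cutpoint".

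Section 8.6.1 also holds the confirmation criterion. The ORR observed over the selected cutpoint in the confirmation set must reach at least the 20th percentile of its posterior predictive distribution from the training set. On the remaining detail, Section 8.0 says "The sSAP will also document the detailed biomarker analysis strategy including determination of the PD-L1_H cut-off selection". sSAP Section 3.6.1 describes the search for a PD-L1 positive cut-off. It gives no rule for two cutpoints and does not repeat the 20th-percentile criterion.

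**The concern.** PD-L1_H is the population for two of the four primary objectives, and there are two ways in which its membership seems open.

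First, if two cutpoints are used, a subject between them is high by one and low by the other. The documents do not say which cutpoint governs objectives 2 and 4, the minimum of 60, or the confirmation criterion. The sSAP, to which the protocol sends the reader, does not say either.

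Second, even with one cutpoint, a Cohort A subject exactly on it is in PD-L1_H by Section 2.1.1 but outside it by a literal reading of Section 8.5.1 and sSAP Section 3.5.1. Read literally, Section 2.1.1 also treats the two cohorts differently.

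At stake would be the membership of two primary ORR estimates, the decision to enlarge Cohort A, and whether the cutpoint counts as confirmed. If these were left open until confirmation data were seen, the choice could follow the results.

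**Working it through.** **1. The plan's own figures.** Section 8.9 assumes 40% prevalence: 150 × 0.40 = 60 in the confirmation set and 75 × 0.40 = 30 in Cohort B. Both reproduce. Exact (Clopper-Pearson) 95% intervals reproduce six of the eight rows of protocol Table 10, for example 21/60: 23.1 to 48.4, and 12/30: 22.7 to 59.4. The other two differ by 0.1 in the lower limit only (18/60: 18.8 computed, 18.9 printed; 8/30: 12.3 computed, 12.2 printed).

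**2. One cutpoint or two.** Sections 2.1.1, 8.5.1 and 8.7 state the base rule with one cutpoint. Sections 3.1 and 8.6.1 state an exception together with its trigger. A rule with a disclosed exception is not a contradiction. What is missing is how the exception maps onto the PD-L1_H label.

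**3. Minimum of 60.** Reaching 60 needs a prevalence of 60/150 = 40% with 150 confirmation subjects, or 60/180 = 33.3% at the cap of 280 (280 − 100 = 180). Assume, for illustration, 60% over the positive cutpoint and 30% over the high positive one.
- Positive: 60/0.60 = 100 confirmation subjects, so no enlargement.
- High positive: 60/0.30 = 200, beyond the cap; the cap yields 180 × 0.30 = 54, and 150 subjects yield 45.

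The cost is precision near 35% ORR:

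| High-positive subjects | Responders | Exact 95% CI (%) | Width (points) |
|---|---|---|---|
| 60 (planned) | 21 | 23.1 to 48.4 | 25.3 |
| 54 (at cap) | 19 | 22.7 to 49.4 | 26.7 |
| 45 (no enlargement) | 16 | 21.9 to 51.2 | 29.3 |

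The plan already accepts about 30 subjects for the Cohort B estimate. Enlargement is also permissive, and Section 8.1 lets the size of the confirmation set depend on PD-L1_H prevalence.

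**4. Confirmation criterion.** It is worded for the results at a given cutpoint. With two cutpoints it yields two answers to two questions. A simulation measured how often they differ (training 100, confirmation 150, nested groups, Beta(1,1) prior, cutpoints fixed in advance, same true ORRs in both sets; prevalences and ORRs assumed). Each check passed in about 81% to 85% of trials, and exactly one passed in 12% to 20%. That is sampling noise between two imperfect checks. Discordance was slightly higher when the upper group had no better ORR than the other positives:

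| Prevalence, positive/high | No enrichment (35/35) | Enrichment |
|---|---|---|
| 40/20 | 16.1% | 14.5% |
| 60/30 | 16.6% | 15.0% |
| 60/40 | 13.2% | 11.8% |

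It therefore does not measure harm from an undefined label.

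**5. Boundary.** Section 3.1 refers objectives 2 and 4 to the definitions in Section 2.1. The only explicit assignment rule there sends every subject to one group or the other: at or over the cutpoint, or under it. The same paragraph then refers to the same Cohort A group as *above* the expected cutpoint, so the word is used loosely. Section 8.6.1 treats *above* and *below* as complements when it defines PPV and NPV. sSAP Section 3.6.1 does the same for sensitivity and specificity and speaks of a binary classifier. A strict reading would put tied subjects in neither group, which fits none of these uses.

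The number of ties is not given. Suppose 6 of 60 subjects with 21 responders (35.0%) lie on the cutpoint. Dropping them gives 19/54 = 35.2% if 2 of the 6 responded, and 21/54 = 38.9% (25.9 to 53.1) if none did. Even on the strict reading the minimum of 60 need not fail. With 2% of subjects tied, prevalence is 38% and 60/0.38 = 157.9, so 158 confirmation subjects suffice, under the 180 available. A shortfall at the cap needs more than 40% − 33.3% = 6.7% of subjects tied.

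**The case for a change.** The best case for acting is that the confirmation set exists to check a rule fixed beforehand. Section 2.1.1 withholds its PD-L1 assays until the cutpoint is set, and Section 8.6.1 attaches a pass criterion. An estimate also needs a fixed population, so the absence of hypothesis testing is not a full answer. Population definitions are what gets programmed, the protocol points to the sSAP for detail that the sSAP does not supply, and a sentence or two would close the gap.

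Some of this stands. If the two-cutpoint option is used, the documents do not rank the two, and the boundary wording is uneven. But the number of cutpoints is decided from the training data, before confirmation samples are assayed, and Section 8.2 keeps the study team blinded to subject-level PD-L1 results. Reporting ORR and the criterion at both cutpoints leaves no favourable choice to make in private. Naming one as primary is a reasonable preference, but statisticians can fairly differ on it when there is no alpha to allocate (Section 8.8). The sSAP describes itself as a companion to the protocol, so the 20th-percentile criterion remains in force without being repeated there.

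**Conclusion.** No change follows. This is an ambiguity in a conditional branch plus loose boundary wording, which analysts would fill sensibly: report each cutpoint that is carried forward, and apply the at-or-above rule of Section 2.1.1 in both cohorts, fixed when the cutpoint is set. In the 60%/30% illustration, the unclear enrolment rule costs 1.4 points of interval width at the cap (26.7 − 25.3) and 4.0 points without enlargement (29.3 − 25.3). The tie effect depends on an unknown number of subjects exactly on the cutpoint. All Comer results are untouched, no hypothesis is tested, and the plan's sample-size figures reproduce to within 0.1 point.

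The conclusion rests on reading *above* as shorthand and on both cutpoints being reported if two are used. It would be weaker if only one of two cutpoints were reported, chosen after the confirmation data were seen; nothing in the plan suggests that.

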8.6.2 Statistical Methods for Safety Analyses

Safety and tolerability will be assessed by clinical review of all relevant parameters including AEs, laboratory tests, and vital signs. Summary statistics (e.g., counts, percentage, mean, standard deviation) will be provided for the safety endpoints as appropriate. The 95% CI for the incidence rate of Grade 2 or higher AEs with an immune etiology (irAEs) and the incidence rate of Grade 4/5 AEs will be provided as appropriate. The All Comer group and the PD-L1_H subgroup will be summarized separately for Cohort A and Cohort B.

8.6.3 Demographic and Baseline Characteristics

Baseline characteristics will be assessed by the use of tables and/or graphs. No statistical hypothesis tests will be performed on these characteristics. The number and percentage of subjects screened, enrolled, primary reasons for screening failure, and discontinuation will be displayed. Demographic variables (e.g., age, gender), baseline characteristics, primary and secondary diagnoses, and prior and concomitant therapies will be summarized either by descriptive statistics or categorical tables. The All Comer group and the PD-L1_H subgroup will be summarized separately for Cohort A and Cohort B.

8.7 Interim Analyses

An interim analysis will be performed after 100 subjects in Cohort A have been enrolled and followed up for at least 4 months to determine a PD-L1 expression cutpoint based on PD-L1 biomarker and tumor response data. The results of this analysis will be presented to the study team without unblinding anyone to individual results. The efficacy data from the interim analysis may facilitate further interactions with regulatory agencies.

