2.1.2 Trial Diagram at Individual Subject Level

This section applies to all subjects who have enrolled to the study. The study includes a 28-day Screening Period, a Study Treatment Period and a Disease/Survival Follow-up Period. Subjects must have measurable disease per RECIST 1.1, as confirmed by the BICR, and must have provided adequate tumor tissue samples in order to be eligible. After an eligible subject is enrolled, the subject will receive pembrolizumab monotherapy 200 mg Q3W via intravenous (IV) infusion until confirmed disease progression as assessed by the investigator, unacceptable toxicity, death, withdrawal of consent, or having received 35 administrations (approximately 2 years) of pembrolizumab treatment without disease progression. In order to prevent premature study treatment discontinuation due to pseudoprogression, immune-related RECIST (irRECIST) will be used for confirmation of disease progression (refer to Section 7.1.2.6.7 for details). Decisions regarding stopping pembrolizumab after a confirmed complete response (CR) and guidelines on retreatment are detailed in Section 7.1.5.2.1.

During study treatment period, subject will have clinic visits Q3W for safety assessments and pembrolizumab infusion. Imaging-based disease assessments will occur every 9 weeks (Q9W) from study entry until Week 54 and every 12 weeks (Q12W) thereafter until disease progression is determined by the investigator per irRECIST, subject's death, withdrawal of consent, initiation of a new anti-cancer therapy, study completion or early termination. Cancer antigen 125 (CA125) will be collected at baseline and at the time of each imaging assessment, However, CA125 should not be used by the investigator to determine disease progression in this study. The trial diagram at subject level is depicted in [Figure 2](#) in Section 2.2.

Specific procedures to be performed during the trial, as well as their prescribed times and associated visit windows, are outlined in the Trial Flow Chart - Section 6.0. Details of each procedure are provided in Section 7.0 – Trial Procedures.

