
e. For women of reproductive potential, a urine or serum pregnancy test should be performed within 72 hours prior to each cycle of trial treatment, and 30 days post-treatment. Additionally, if urine test is positive or is not evaluable, a serum test is required. Subjects must be excluded/discontinued in the event of a positive test result. Monthly pregnancy testing should be conducted as per local regulations where applicable.
 
f. ECOG Performance Status and Laboratory tests for screening and determining eligibility are to be performed within 10 days prior to the first dose of trial treatment.
 
g. CBC with diff and Chemistry to be performed every cycle through Cycle 6 and then every other cycle thereafter.
 
h. UA and thyroid function tests will be performed every other cycle.
 
i. Both PK and Anti-pembrolizumab Samples: pre-dose (trough) PK and anti-pembrolizumab antibody samples will be collected at within 24 hours before infusion at Cycles 1, 2, 4, 6, 8 and every 4 cycles thereafter.
 
j. PK Samples: additional post-dose (peak) PK samples will be drawn within 30 minutes after end of pembrolizumab infusion at Cycles 1 and 8. An additional single PK sample should be drawn at; 24 hours (\pm 4 hours) [Day 2], between 72 and 168 hours[Day 4-8] and 336 hours (\pm48 hours) [Day 15] after Cycle 1 dosing.
 
k. Sample should be drawn for planned genetic analysis of DNA and drug response unless there is either a documented law or regulation prohibiting collection, or unless the IRB/IEC does not approve of the collection of the sample for these purposes. Leftover extracted DNA will be stored for future biomedical research if the subject signs the ICF for FBR.
 
l. Whole blood samples for correlative studies (DNA and RNA) should be collected pre-dose on Day 1 of Cycle 1, Cycle 2, and Cycle 3, and again at treatment discontinuation. Whole blood for Biomarker Samples (plasma and serum) to be collected pre-dose on Day 1 of Cycle 1 only.
 
m. Blood for tumor biomarker CA-125 at screening and at the time of each tumor imaging assessment
 
n. Newly obtained tissue is preferred. If a newly obtained tumor tissue sample cannot be obtained, an archived tumor tissue sample can be submitted. Samples that are formalin-fixed paraffin-embedded must be provided to the designated central laboratory in order to be eligible. Adequacy and quality of the archived tissue samples must be confirmed by the central laboratory before enrollment
 
o. Screening tumor imaging will be performed within 28 days prior to the date of allocation. Confirmation of baseline measurable disease per RECIST 1.1 by the central imaging vendor is required prior to subject allocation.
 
p. The first on-study imaging time point will be performed at 9 weeks (63 days \pm 7 days) calculated from the date of allocation during the first 54 weeks, and every 12 weeks (84 days \pm 7 days) thereafter, or earlier if clinically indicated.
 
q. In subjects who discontinue study therapy without confirmed PD by the site per irRECIST, tumor imaging should be performed at the time of treatment discontinuation (\pm 4 weeks). If previous tumor imaging was obtained within 4 weeks prior to the date of discontinuation, then additional tumor imaging at treatment discontinuation is not required.
													

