Interim Analyses	An interim analysis is planned at 4 months after the first 100 subjects have been enrolled in Cohort A, which will be used as the training set. IA will evaluate clinical activity and the correlation of PD-L1 in tumor tissue samples in the training set to facilitate the PD-L1 expression cut-off selection.
Multiplicity	No multiplicity adjustment has been planned.
Sample Size and Power	Cohort A-All Comer group include the first 180 enrolled subjects fulfilling the eligibility of Cohort A. A minimum of 75 subjects will be enrolled for the subgroup with a PFI/TFI of 3 to <6 months and the subgroup with a PFI/TFI of 6 to 12 months. The first 100 enrolled Cohort A subjects will be used as the training set for determining a PD-L1 expression cut point. The additional 150 enrolled Cohort A subjects will be in the confirmation set, therefore, the study will enroll approximately 250 Cohort A subjects regardless of the PD-L1 status. The exact number of subjects enrolled in the confirmation set will depend on the prevalence of the PD-L1 _H as determined by the biomarker analysis. Approximately 75 subjects will be enrolled in Cohort B.

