8.6 Statistical Methods

8.6.1 Statistical Methods for Efficacy Analyses

This section describes the statistical methods that address the primary and secondary objectives. Methods related to exploratory objectives will be described in the sSAP.

Data from the training set (first 100 subjects in Cohort A) will be evaluated for biomarker analysis and cut point determination. The analysis of confirmation set (150 subjects in Cohort A) will focus on verifying the response rate above the cut point is consistent with predictions made based on the training set data used to set the cut point via the interim analysis. Results for the cut point will be considered confirmed in a direction that supports the proposition of enrichment provided the observed response rate in the confirmation set for subjects above the selected cut point is greater than or equal to the 20th percentile of its posterior predictive distribution as determined using the training set at the time the cut point is set. In other words, consistency of effect is defined as not belonging to the lower 20% of the training set's predictions for enrichment associated with use of the cut point.

Efficacy will be evaluated in the All Comer group and the PD-L1_H subgroup for Cohort A and B respectively. For the primary efficacy endpoint, the ORR based on RECIST 1.1 by the blinded central imaging vendor review, the point estimate, and 95% CI (as determined by the upper and lower 97.5% one-sided confidence bounds) will be provided using an exact binomial distribution. Subjects without response data will be counted as non-responders. Secondary efficacy evaluations of ORR based on RECIST 1.1 by investigator review, and

ORR based on modified RECIST 1.1 by blinded central imaging vendor review will also be conducted using the same methodology as for the primary efficacy analysis.

Duration of response by blinded central imaging vendor review and investigator review will be summarized using KM method in all responders.

For PFS and OS, KM curves, median estimates, and survival at 6, 12 and 18 months based on the KM curves (95% CI is based on Greenwood's formula) will be provided as appropriate. Subjects without efficacy evaluation data or without survival data will be censored at Day 1. The DCR will be summarized at the end of the trial. The restricted Mean Survival Time estimate of PFS and OS will also be calculated and plotted over time.

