3.4.1 Efficacy Endpoints

Primary

- **Objective response rate (ORR) - per RECIST 1.1 assessed by BICR**

Objective Response Rate (ORR), defined as the proportion of subjects in the analysis population who have confirmed complete response (CR) or partial response (PR) at any time during the study.

Secondary

- **Duration of Response (DOR) - per RECIST 1.1 assessed by BICR and by investigator**

Duration of response (DOR), defined as the time from first documented evidence of response to disease progression in subjects who achieve a confirmed PR or CR.

- **Progression-free Survival (PFS) - per RECIST 1.1 assessed by BICR and by investigator**

Progression-free survival (PFS), defined as the time from the first day of study treatment to the first documented disease progression or death due to any cause, whichever occurs first.

- **Overall survival (OS)**

Overall survival (OS), defined as the time from the first day of study treatment to death due to any cause.

- **Disease Control Rate (DCR) - per RECIST 1.1 assessed by BICR**

Disease Control Rate (DCR), defined as the percentage of subjects who have achieved confirmed CR or PR or have demonstrated SD for at least 24 weeks prior to any evidence of progression.

Exploratory

- **Progression-free survival (PFS) – irRECIST assessed by BICR**

Progression-free-survival (PFS) is defined as the time from first day of study treatment to the first confirmed disease progression or death due to any cause, whichever occurs first.

ORR and DOR per irRECIST by BICR are also the exploratory efficacy endpoints.

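### The rule for confirming the PD-L1 cutpoint compares responses read at 8 months or more with a prediction frozen from data that may have only 4 months' minimum follow-up, so it passes more easily than its nominal 80%

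*Combined protocol and SAP*

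**What the plan says.** **Interim timing.** Protocol 8.7 and the supplemental SAP (sSAP) 3.7 place the cutpoint analysis after 100 Cohort A subjects have been "enrolled and followed up for at least 4 months". Protocol 2.1.1 agrees: "Clinical cut-off for interim analysis will be at least 4 months after the one-hundredth Cohort A subject has been enrolled". The summary tables in protocol 8.1 and sSAP 3.1 leave out the qualifier: "An interim analysis is planned at 4 months after the first 100 subjects have been enrolled in Cohort A".

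**Final timing.** Protocol 2.1.1, for each study population including Cohort A PD-L1_H: "the clinical cut-off for the final analysis of the primary endpoint ORR will be at least 8 months after the last subject".

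**Confirmation rule.** Protocol 8.6.1 treats the cutpoint as confirmed if the confirmation-set response rate above it is at or above the 20th percentile of its "posterior predictive distribution as determined using the training set at the time the cut point is set".

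**Scans and confirmation of response.** Protocol 2.1.2: "Imaging-based disease assessments will occur every 9 weeks (Q9W) from study entry until Week 54". Flow chart 6.1 runs the clock from allocation, with a 7-day window either side: "calculated from the date of allocation during the first 54 weeks". Under 7.1.2.6.2 a response is confirmed at least 4 weeks after it is first seen, or at the next scheduled scan.

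**Response definition.** sSAP 3.4.1 counts "confirmed complete response (CR) or partial response (PR) at any time during the study". The definition in protocol 8.4.1 omits the word confirmed.

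**The concern.** The rule asks whether the confirmation set performs as the training set predicted. That is a fair question only if the two response rates measure the same thing. Here the prediction may be built on 4 months' minimum follow-up, while the rate tested against it has at least 8. A subject who will respond, but whose response has not been seen or confirmed at the interim cut, enters the training data as a non-responder. The error runs one way: the predicted rate is too low, and so is its 20th percentile.

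At stake is the meaning of the statement that the cutpoint was confirmed. The rule is meant to exclude the lowest 20% of predictions. If the benchmark is depressed it excludes less than that, and a pass says correspondingly less about enrichment. I found no provision that requires a minimum number of scans at the interim, adjusts for the gap, or recomputes the prediction later.

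**Working it through.** **1. The plan's own figures.** 0.40 × 150 = 60 PD-L1_H subjects in the confirmation set (protocol 8.9), and likewise 0.40 × 100 = 40 in training. The documents give no prior, so I assume a flat Beta(1,1).

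- Training responders: X ~ Binomial(40, p(1 − u)), where p is the true response rate and u the share of training responses not yet counted.
- Prediction for the confirmation set: Beta-binomial(60; 1 + X, 41 − X), with 20th percentile q(X).
- Pass if Y ≥ q(X), where Y ~ Binomial(60, p). Average over X.

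With p = 35% and u = 0 the pass probability is 81.2%, against 80% nominal. A Jeffreys prior gives 81.8%.

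**2. What can be seen at the minimum cut.** Four months is 4 × 30.4375 = 121.75 days; 8 months is 243.5 days. Week 18 is day 126 (window 119 to 133), Week 18 plus 4 weeks is day 154, and Week 27 is day 189.

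Accrual is inferred from the trial summary: 48 months in all less 36 months of survival follow-up leaves 12. Then 250/12 = 20.8 Cohort A subjects per month, or 0.684 per day. The number not yet at day d is the 100th subject plus those enrolled in the preceding (d − 121.75) days.

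| Milestone | Day | (d − 121.75) × 0.684 | Of 100 not yet there | Accrual over 24 to 9 months |
|---|---|---|---|---|
| Week 18 scan, nominal | 126 | 2.9 | 3 | 2 to 4 |
| Week 18 response confirmed at +4 weeks | 154 | 22.1 | 23 | 12 to 30 |
| Week 27 scan | 189 | 46.0 | 47 | 24 to 62 |

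The immaturity therefore comes mainly from Week 18 responses awaiting confirmation and from Week 27 scans not yet done.

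**3. Effect on the rule.** The same true rate is used in both sets.

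| Training responses uncounted | Pass, true rate 35% | Pass, true rate 25% |
|---|---|---|
| 0% | 81% | 81% |
| 10% | 89% | 88% |
| 20% | 95% | 93% |
| 30% | 98% | 96% |

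To see the mechanism: 14 of 40 training responders (35%) set the bar at 17 of 60. With 20% uncounted, 14 becomes about 11, and the bar drops to 12 of 60.

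**4. Is 10% to 30% a plausible range?** The documents give no response timing for ovarian cancer, so I assumed three splits of first response over Weeks 9/18/27/36, with 12-month accrual and a true rate of 35%.

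| Assumed split and scoring | Visible, training at 4 months | Visible, confirmation set at 8 months | Relative shortfall | Pass as planned | Pass with training at 8 months |
|---|---|---|---|---|---|
| 75/15/7/3, unconfirmed counted | 0.94 | 1.00 | 6% | 87% | 81% |
| 60/22/12/6, confirmed at +4 weeks | 0.81 | 0.99 | 18% | 94% | 82% |
| 40/30/18/12, confirmed at next scan | 0.57 | 0.95 | 41% | 99% | 83% |

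Matching the minimum follow-up brings the rule back close to 80% in every case.

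**The case against.** **The cut is a minimum, and the Week 18 scan is nearly in reach.** A reader might infer that the training set is scored before its second scan. The documents do not support that. The clock starts at the 100th subject, day 122 lies inside the Week 18 window, and only about 3 of 100 would lack that scan. A Week 9 response can be confirmed by Week 13, before the cut even for the last subject. This stands, and it limits the size. It does not remove the gap, because a later cut is permitted but not required.

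**Cutpoint misplaced.** This too is tempting and is not shown. If the lost responses are unrelated to PD-L1, sensitivity, the ranking of cutpoints and the ratio of PD-L1_H to overall response (35/25 = 1.4) do not change. Only NPV rises. On the plan's figures the rate below the cutpoint is (25 − 0.40 × 35)/0.60 = 18.3%, so NPV is 81.7%; a 20% loss makes it 85.3%, still short of the illustrative 90%. A shift in a known direction would need response timing to depend on PD-L1, on which the documents are silent.

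**Definition and timing of response.** It is not stated that the interim uses confirmed response, and the melanoma data in protocol 4.1.2 put most responses at the first scan, though some came as late as 11 months. Both points reduce the loss; the most favourable case above still gives 87%.

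**Offsetting bias.** Choosing a cutpoint on the training data tends to inflate its apparent response rate, which pushes the other way. That is a separate error of unknown size, and nothing in the plan makes the two cancel.

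**Stakes.** No formal test is planned, and the rule is lenient by construction. The primary PD-L1_H rate and exact interval come from the confirmation set alone at 8 months or more, so they are not biased. All of this stands; the point concerns only the claim of confirmation. The sSAP does not repeat the rule, but it presents itself as a companion to the protocol and does not withdraw it.

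**Conclusion.** As written, protocol 8.6.1 compares response rates of unequal maturity, and the inequality favours declaring the cutpoint confirmed. With 10%, 20% or 30% of training responses uncounted, the pass probability rises from 81% to 89%, 95% or 98% at a true rate of 35% in both sets, and from 81% to 88%, 93% or 96% at 25%.

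The direction follows from the documents. The size rests on assumptions: response timing, the flat prior, 40% prevalence in both sets, accrual inferred from the stated trial length, and whether response must be confirmed at the interim. It would be smaller if the interim cut were taken later than the minimum, if most responses came at the first scan, or if unconfirmed responses were counted.

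A reader might go further and infer that the PD-L1_H response estimate is biased or that the cutpoint itself is wrong. Neither is supported.

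**What to change.** Keep the interim timing, and keep the cutpoint fixed once it is chosen. In protocol 8.6.1, replace the clause that ties the prediction to the moment the cutpoint is set. State instead that the posterior predictive distribution is computed from training-set responses with the same minimum follow-up as the confirmation set (8 months) and the same confirmed-response definition (sSAP 3.4.1). Repeat the rule in sSAP 3.6.1, and bring the ORR definition in protocol 8.4.1 into line with sSAP 3.4.1.

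The cost is one reanalysis and a numerical benchmark that is final later than now planned. It need not hold anything up. On 12-month accrual the 100th subject is enrolled at 100/20.8 = 4.8 months, so the training set reaches 8 months' follow-up at about month 12.8. The confirmation set reaches it at about month 12 + 8 = 20.

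Postponing the interim itself would be a worse trade. A cut 28 weeks after the 100th subject would bring the cutpoint at about month 11.2 of 12 and leave little time for the prevalence-based increase of Cohort A to 280. If accrual took 9 months, it would come after the 250th subject.
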